6.3 Analysis Windows

All assessments will be summarized using analysis windows. The terminology of unscheduled will be applied to assessments that are outside an analysis window regardless, of the nominal label associated with the assessments in the EDC system.

All data (scheduled and unscheduled visits) will be presented in the subject listings; however, unless noted otherwise, only data from assessments within analysis windows will be included in the summaries, statistical analysis, and calculation of derived parameters.

In part C, the analysis window will be +/-3 days for the scheduled visits from Day 8 through Day 29, ±7 days for scheduled visits between Day 57 through Day 169 as defined below.

Nominal Day	Start (days)	Stop (days)
8	5	11
15	12	18

Nominal Day	Start (days)	Stop (days)
22	19	25
29	26	32
57	50	64
85	78	92
113	106	120
140	133	147
155	148	162
169	163	175

If the scheduled visit is outside of the analysis window, data will not be counted in the summary tables. In each part, the summary tables by the scheduled visit will only use data recorded for the scheduled visit. Data collected at the unscheduled visit will not be counted in the summary table, however will be included in the subject listings.

General Selection Process for Multiple Records in an Analysis Window

In general, if multiple, valid, non-missing observations exist at a visit or collection time point then records will be chosen based on the following:

- The record closest to the nominal time point in question, or,
- The later record if the two visits are equidistant from the time point, or,
- The average (arithmetic mean) if there is more than one record at the time point (generally applies to assessments done in triplicate).

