In Part C, subjects will enter the research center on Day -2 and remain resident in the research facility to undergo safety, PD, PK and diseases assessments through the morning of Day 2 of Part C, after which they will be discharged home. Subjects will return on an outpatient basis and undergo safety, PK/PD and disease assessments as described in the schedule of assessments. In addition, telephone assessments for safety and disease assessment will be performed on a weekly (during Month 1) and monthly basis (Months 2 through 5) where no clinic visit is scheduled. In such a case that the dose is reduced, the subject should be scheduled for a clinic visit to occur within approximately 2 weeks of the dose reduction. Following completion of the [REDACTED] dosing period, or in the case of early discontinuation from the study, subjects will return 2 and 4 weeks after the final dose for follow-up visits to undergo safety, PK/PD and diseases assessments and end of study procedures. In cases where the subject is unable to return to the clinic due to significant physical or geographic limitations, or at the Investigator's discretion, a nurse may be sent to the subject's home and the study visit procedures performed in the subject's home, except for the day 29 visit which must be done within the research center.

Adverse events will be assessed throughout the study duration in each Part and will be recorded in the case report form when reported.

Study procedures are further described in [Table 1](#) for Part A and [Table 2](#) for Part C and in [Section 6](#).

Duration of Study Participation:

The duration of study involvement for each subject will be up to approximately 36 days for Part A (including up to 30 days for screening), and 169 days for Part C.

PROTOCOL SYNOPSIS (CONTINUED)

Number of Subjects per Group:

Up to [REDACTED] will be enrolled. Subjects who demonstrate a pressor effect in Part A, who complete Part A, and who remain otherwise eligible are eligible to participate in Part C.
[REDACTED]

Study Population:

This study will enroll adult subjects with confirmed nOH due to MSA, PAF, or Parkinson's disease and who meet other inclusion and exclusion criteria defined below.

Inclusion Criteria:

1. Male or female at least 40 years of age.
2. Subject is able to communicate well with the Investigator and understands the expectations of the study.

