In the case where a subject develops the presence or worsening of supine hypertension (as determined by the Investigator with agreement from the Sponsor) or other adverse events suggesting intolerance, the dose can be withheld for 3 days and resumed at a dose level 50% (rounded up to the nearest 1 mg) of the prior dose level. If supine hypertension or other adverse events persist after the dose has been reduced, dosing in that subject should be discontinued and appropriate alternative therapy and care provided to the subject as determined by the principal investigator.

In Part A, subjects will be administered study drug by qualified study personnel under the supervision of the Investigator. Study personnel will observe and record date and time of dosing and in the event any deviations or incomplete administrations will be noted in the source records.

In Part C, subjects will be administered study drug by qualified study personnel under the supervision of the Investigator on Day 1 and Day 2. On all other dosing days, subjects will record the date and time of their daily dose in a dosing diary. Any dose increases, missed doses, or issues with dosing should be noted in the dosing diary. Site staff will also record any dose increase in the subject's source documents. Subjects are expected to bring the

dosing diary and any empty and/or partially used bottles of study drug to the clinic on their return visits.

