9.3.4 Vital Signs

Vital signs will be summarized in terms of observed values (by time point), changes from baseline (by time point). When multiple values exist for the same nominal time point (e.g., duplicate reading), the average of the readings taken for vital signs will be used in the data analysis. All recorded values for vital signs data will be presented in a by-subject listing. Vital signs outliers will be flagged in the listing (Table 2).

Table 2. Vital Signs Outlier Thresholds

Heart Rate Systolic Blood Pressure		Diastolic Blood Pressure
(bpm) (mmHg)		(mmHg)
<40	<85	<45
>110	>160	>100

A sustained elevation in supine vital signs (the mean value of BP or HR) is defined as the elevation above a given threshold at three or more consecutive on-treatment measurements. For example, elevation at pre-breakfast, pre-lunch measurement on one visit as well as pre-breakfast measurement at the subsequent visit will be considered as

sustained elevation; on the other hand, elevation at pre-breakfast but not at pre-lunch for 3 consecutive visits will not constitute as "sustained" elevation.

Categorical elevated vital signs are defined in Table 3 and Table 4. Number of subjects with elevated vital signs will be summarized by visits in Part C.

Table 3. Threshold for Elevated Supine Vital Sign

Measurements	Thres	hold
Increase from Baseline in SBP	≥ 20	≥ 30
(mmHg)		
Increase from Baseline in DBP	≥ 10	≥ 20
(mmHg)		
Increase from Baseline in HR	≥ 10	≥ 20
(bpm)		
Post-baseline value SBP (mmHg)	≥ 140	≥ 160
Post-baseline value DBP (mmHg)	≥ 90	≥ 100
Post-baseline value HR (bpm)	≥ 100	≥ 120

Table 4. Combined Criteria for Elevated Supine Vital Sign

Combined Criteria
SBP ≥ 140 and Increase from Baseline ≥ 20
DBP ≥ 90 and Increase from Baseline ≥ 10
HR ≥ 100 and Increase from Baseline ≥ 20
SBP ≥ 160 and Increase from Baseline ≥ 20
DBP ≥ 100 and Increase from Baseline ≥ 10
HR ≥ 120 and Increase from Baseline ≥ 20

In addition, the following will also be summarized.

- a decrease in systolic blood pressure (a mean value of SBP) from supine to standing of ≥ 20 (and 30) mmHg and/or
- a decrease in diastolic blood pressure (a mean value of DBP) from supine to standing of ≥ 10 mmHg
- an increase in heart rate (a mean value of HR) from supine to standing of ≥ 30 bpm and/or
- an observed HR ≥ 120 bpm upon standing

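### Supine pressures taken on Part C days that fall in no SAP window, including visits after a dose reduction, are left out of every elevated-supine-BP count.

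*SAP*

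**What the plan says.** **Protocol.** Section 1.4 lists an increase in BP among the important potential risks, and section 3.4.2 includes supine blood pressure in the safety assessments. Section 5.2 provides that, on new or worsening supine hypertension "or other adverse events suggesting intolerance, the dose can be withheld for 3 days" and then resumed at half the previous level. It adds: "If supine hypertension or other adverse events persist after the dose has been reduced, dosing in that subject should be discontinued". The Part C text of the Synopsis states: "In such a case that the dose is reduced, the subject should be scheduled for a clinic visit to occur within approximately 2 weeks". Table 2 has no column for that visit, and no procedures are listed for it.

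**SAP 6.3.** Status is set by date: "The terminology of unscheduled will be applied to assessments that are outside an analysis window regardless" of the label in the data capture system. Unless noted otherwise, "only data from assessments within analysis windows will be included in the summaries, statistical analysis, and calculation of derived parameters". If a window holds several records, the one nearest the nominal day is kept, or the later one if two are equally near. The section then limits by-visit tables to data recorded for the scheduled visit, and adds: "Data collected at the unscheduled visit will not be counted in the summary table, however will be included in the subject listings". SAP 6.1 likewise restricts summaries and derived parameters to scheduled visits.

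**SAP 9.3.4.** Thresholds for elevated supine vital signs are in Tables 3 and 4. The planned output is: "Number of subjects with elevated vital signs will be summarized by visits in Part C". Table 14.3.11.2 is also by visit. Sustained elevation means three or more consecutive on-treatment measurements above a threshold. All values are listed, with outliers flagged. The section makes no exception for unscheduled readings.

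**The concern.** Supine hypertension is the obvious hazard of a pressor drug, and there is no data monitoring committee (Protocol 8.5). Two kinds of reading carry much of the information: an off-schedule reading that prompts a dose reduction, and a later one that shows whether the hypertension persisted, which is the protocol's stated ground for stopping dosing. Both can fall on a day with no window. They are then absent from every threshold count, and no count of subjects elevated at any time on treatment exists to pick them up. The readings at risk come disproportionately from subjects whose dose was reduced.

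The SAP is fuller elsewhere. Exposure is summarised overall as well as by visit (9.3.1), and laboratory shifts are taken to the worst increase and worst decrease (Tables 14.3.10.1 and 14.3.10.2). Supine pressure has no equivalent.

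**Working it through.** **Inputs.** Windows: SAP 6.3. Last dose Day 140, with on-treatment clinic visits after Day 2 on Days 15, 29, 85 and 140 and telephone assessments on Days 8, 22, 57 and 113: Protocol Table 2. About two weeks is read as 14 days, an assumption; 10 and 17 days were also tried.

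**1. Rebuild the windows.** Nominal day ±3 up to Day 29 and ±7 from Day 57 reproduces every on-treatment row. Only Day 169 differs (printed 163-175, against 162-176). It lies after the last dose and has no bearing here.

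**2. Find the gaps.** Days 5-32 are continuous. After that:

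| Gap | Days |
|---|---|
| 33-49 | 17 |
| 65-77 | 13 |
| 93-105 | 13 |
| 121-132 | 12 |
| Total | 55 |

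This is 55 of the 100 days from Day 33 to Day 132, and 55 of the 136 days from Day 5 to Day 140 (40%). Days 3 and 4 also lie in no window.

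**3. Follow a reading taken on a gap day.** It is unscheduled by the date rule of 6.3, so it is out of summaries and derived parameters. No exception in 9.3.4 brings it back. It therefore reaches the listing but no Table 3 or Table 4 count. Sustained elevation is a derived parameter, so the same exclusion applies, although 9.3.4 does not address it.

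**4. Follow a reading from an extra visit inside a window.** Under the window rule of 6.3 it is eligible. Under 6.1 and the closing rule of 6.3 it is not, because it was not recorded for the scheduled visit. Even under the window rule, the nearest-record rule can remove it: with the scheduled assessment on Day 57 and an extra visit on Day 60, the distances are 0 and 3 days, and the extra reading is dropped.

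**5. How much of the calendar is exposed.**
- Reductions on Days 2-14, 15-28, 71-84 and 126-139 have a Table 2 clinic visit within 14 days that could serve as the follow-up: 13 + 14 + 14 + 14 = 55 of 138 possible days. (This 55 is unrelated to the 55 gap days.)
- The other 83 (Days 29-70 and 85-125) need an extra visit. Spread evenly over the next 14 days, that gives 83 × 14 = 1,162 landing days, of which 652 (56%) are in a gap. With a 10-day limit the share is 523/980 = 53%, and with 17 days 709/1,309 = 54%.
- Over all 138 reduction days, with Table 2 visits used where they can be: 652/(138 × 14) = 652/1,932 = 34%.
- If instead no Table 2 visit serves and the lag is fixed, a visit exactly 14 days after a reduction on Days 3-126 is in a gap for 55/124 = 44% of days. At exactly 7 days (reductions on Days 3-133) it is 55/131 = 42%.

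These are shares of calendar days, not of subjects or readings.

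**6. Direction.** A subject counts as elevated at any time if the highest reading reaches the threshold. Adding readings cannot lower that maximum, so leaving readings out can only lower this count or leave it unchanged. Sustained elevation has no fixed direction: an extra high reading can complete a run of three, and an extra normal one can break it.

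**The case against.** A reader might infer that every post-reduction visit is unscheduled, so that subjects with supine hypertension disappear from the safety results. The documents do not support this.

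- Status depends on date. Days 5-32 have no gap, and a Table 2 clinic visit can serve as follow-up for 55 of 138 possible reduction days.
- An elevation seen at a scheduled in-window visit stays in the Table 3 and Table 4 counts.
- Protocol 7.5 requires abnormal vital signs to be recorded as adverse events when they are symptomatic or judged clinically significant and meet the definition. Treatment-emergent events are counted to 30 days after the last dose with no visit window (SAP 9.3.2). Hypertension serious enough to reduce the dose may well be counted there.
- The protocol says the visit should be scheduled, reductions can follow other adverse events, and supine pressure is not expressly listed for the visit.
- The SAP plans no count of subjects ever elevated, so the gap is an omitted summary and not an error in a planned one.

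All of this stands and limits the point without removing it. Adverse-event capture depends on symptoms or investigator judgement, so it does not replace a count against fixed thresholds. Listings give no numerator or percentage. SAP 9.2.3 counts outliers in 24-hour SBP, but those sessions are set 72 to 48 hours before the Day 15, 29, 85 and 169 visits. On the nominal calendar they start around Days 12-13, 26-27, 82-83 and 166-167, none of them in a gap.

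**Conclusion.** The point holds in limited form. Supine pressures recorded on the 55 gap days enter no Table 3 or Table 4 count and, under SAP 6.1 and 6.3, no derived parameter. For extra visits inside a window, the SAP does not settle whether the reading counts.

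The calendar share of post-reduction visits that would land in a gap is about 34% to 44%. That range assumes reductions spread evenly over the treatment period, the 14-day (or 7-day) reading of the visit request, and the two treatments of Table 2 visits shown above. It must not be read as a share of subjects missed. The effect on subject counts cannot be computed, because the documents give no reduction rate and the sample size is redacted. It may be small. The change is still worth making: it is cheap, and it closes a gap in a named safety endpoint that can only hide elevations when subjects ever elevated are counted.

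**What to change.** 1. In SAP 9.3.4 and Table 14.3.11.2, keep the by-visit rows. For each Table 3 and Table 4 threshold add a row, *at any time on treatment*, using every recorded supine reading from first to last Part C dose, scheduled or unscheduled, in or out of window.
2. State in SAP 6.1 and 6.3 that the exclusion does not apply to this row.
3. Reconcile the scheduled-visit rule with the window rule, so that it is clear whether an extra in-window visit counts in the by-visit rows.
4. State in 9.3.4 that unscheduled readings count in the sustained-elevation run.

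The cost is a few sentences and one row per threshold. No new data are needed, since the rows use only readings that are recorded and listed anyway. The reported frequency of supine hypertension may be slightly higher, and sustained-elevation counts could move either way.

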6.4 Missing Data

In general, missing data will not be imputed. Subjects without post-baseline measurement for a given treatment period will be excluded from the summary statistic (e.g., denominator of the summary statistic) for that time point.

Missing data for the following specific endpoints will be handled as follows:

Primary Efficacy Endpoint

Missing data in the analysis of the primary endpoint is assumed as missing at random (MAR) and will not be imputed in the primary analysis.

Adverse Events (AE)

For graded AE summaries, subjects with an AE and no grade on the CRF will be graded as severe. AEs without assigned relationship to study drug will be counted as AEs related to study drug in the AE summaries.

Missing dates/time for AEs and Concomitant Medications

Missing dates will be handled as follows:

- Complete missing start date will be imputed as the same as first dose date;
- Partial missing start date imputation:
 - Missing start day with same month as first dose: maximum day (1, first dose day);
 - Missing start day with different month as first dose: 1
 - Missing start month with same year as first dose: maximum (January, first dose month);
 - Missing start month with different year as first dose: January
- Complete missing stop date will be considered as ongoing and not imputed;
- Partial missing stop date imputation:
 - Missing stop day: last day of month;
 - Missing stop month with same year as last dose: minimum (December, last dose month);
 - Missing stop month with different year as last dose: December

Missing times will be handled as follows:

• If a start or stop time is missing, the start time is imputed as 1 minute after a.m. midnight (12:01) and stop time is imputed to be 1 min before p.m. midnight (23:59).

Laboratory Data

For non-efficacy laboratory data, a missing baseline value will be replaced with the last available assessment before the first dose, generally the screening assessment. A retest value will be used if the first test is invalidated, e.g., specimen hemolyzed.

Laboratory data that are continuous in nature but are less than the lower limit of quantitation/limit of detection (LOD) will be, in general, imputed as follows:

- A value that is 1 unit less than the LOD will be used for calculation of descriptive statistics if the data are reported in the form of "< x" (x is considered as the LOD).
 More specifically, x−1 is used for data summarization if the data are reported in the form of "< x"; and x.e where e = d−1, will be used for analysis if the data are reported in the form of "< x.d":
- The LOD will be used for calculation of descriptive statistics if the data is reported in the form of "≤x" or "≥x.

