ICH	International Council on Harmonization of Technical Requirements for Registration of Pharmaceuticals for Human Use
IEC	Independent Ethics Committee
IRB	Institutional Review Board
IUD	intra-uterine device
LDH	lactose dehydrogenase
LS	least square
MAO-I	monoamine oxidase inhibitor
MAR	missing at random
MedDRA	Medical Dictionary for Regulatory Activities (MedDRA®)
MSA	multiple system atrophy
NE	norepinephrine

LIST OF ABBREVIATIONS AND DEFINITION OF TERMS

Abbreviation	Description
NET	norepinephrine transporter
nOH	neurogenic orthostatic hypotension
NRI	norepinephrine Reuptake Inhibitor
NYHA	New York Heart Association
OH	Orthostatic Hypotension
OHDAS	Orthostatic Hypotension Daily Activity Scale
OHQ	Orthostatic Hypotension Questionnaire
OHSA	Orthostatic Hypotension Symptom Assessment
PAF	pure autonomic failure
PD	Parkinson's disease
PD	pharmacodynamic(s)
PI	principal investigator
PK	pharmacokinetic(s)
PT	preferred term
QTcF	corrected QT interval
REB	Research Ethics Board
SA	sinus arrhythmia
SAE	serious adverse event
SBP	systolic blood pressure
SERT	serotonin transporter
SOC	system organ class
SOP	standard operating procedure
TEAE	treatment-emergent adverse event
TOEPH	heterogeneous banded Toeplitz structure
WBC	white blood cell count

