9.2.1 Primary Efficacy Evaluation

For Part C, the primary endpoint is the improvement from baseline in the Likert scale "dizziness, lightheadedness, feeling faint, or feeling like you might black out" (OHSA, question 1) at week 4. The scales will be treated as continuous variable, and a summary table including descriptive statistics will be generated. A responder in Part C is defined as a subject who demonstrates at least a 2 unit decrease (improvement) from baseline in the OHSA question 1 at week 4. The proportion of subject who demonstrate \geq 1 unit, \geq 2 units, \geq 3 units, \geq 4 units improvement, no change, and worsen (by 1 and >1 unit) at each visit will be calculated with exact 90% confidence intervals and summarized by visit and dose level per each visit. In addition, OHSA question 1 improvement will be summarized by baseline value categories (baseline OHSA #1 \geq 2).

The example SAS code for summary of proportion of responders is following:

```
proc freq data = xxx;

by timepoint cat;

tables yes_no / binomial(exact) alpha=.1 cl;

ods output BinomialCLs = result_1;

run;
```

Where 'timepoint' is the time points for the measurements, 'cat' is the category of improvement (or no change, worsen) by number of unit, and 'yes_no' is the indicator for subjects in each category.

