9.2.4 Multiplicity Adjustment

Multiplicity adjustment is not applicable since only descriptive summaries are provided.

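### The SAP assumes the Week 4 primary endpoint is missing at random, but plans only an observed-case mean, which that assumption alone does not justify

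*SAP*

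**What the plan says.** SAP 6.4 says "Missing data in the analysis of the primary endpoint is assumed as missing at random (MAR", and the same sentence rules out imputation for the primary analysis. The general rule in that section is that subjects with no post-baseline measurement "will be excluded from the summary statistic (e.g., denominator of the summary statistic) for that time point".

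SAP 9.2.1 names improvement in OHSA question 1 at Week 4 as the primary endpoint and says: "The scales will be treated as continuous variable, and a summary table including descriptive statistics will be generated". It adds responder proportions with exact 90% confidence intervals. SAP 9.2.4 confirms the scope: "Multiplicity adjustment is not applicable since only descriptive summaries are provided". Section 9 calls for no model, imputation, weighting or sensitivity analysis for the Week 4 mean. Appendix 1 has LS-mean layouts, but they are generic templates with a placebo comparison, and no Part C analysis in section 9 calls for them.

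SAP 7.1 defines the ITT set as everyone enrolled in Part C who took at least one dose; a Week 4 score is not required. SAP 6.3 sets the Day 29 window at Days 26 to 32 and adds: "If the scheduled visit is outside of the analysis window, data will not be counted in the summary tables".

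Protocol Table 2 and its footnote on the questionnaires schedule the OHQ on Days 8, 15, 22 and 29. Days 8 and 22 are telephone assessments.

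**The concern.** MAR allows missingness to depend on scores already observed. The missing-data mechanism can then be ignored only if the analysis uses those scores, as a likelihood model or multiple imputation does. A plain mean of the available Week 4 changes does not use them. In general it represents the whole ITT set only if missingness is unrelated to the scores, which is a stronger assumption than the one the SAP states. The plan therefore names an assumption that its own estimator cannot rely on.

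SAP section 1 says the results will guide decisions about further development. Part C is open-label with a single arm, so no control group offsets a shift in the mean. The risk is a biased estimate and not a type I error, because no test is planned.

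**Working it through.** The documents give no figure to reproduce: the sample size, SD and expected dropout for Part C are blacked out. The check is therefore of the estimator, over an assumed range.

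**Inputs.** From the documents: observed-case handling (SAP 6.4), descriptive summary only (9.2.1, 9.2.4), earlier scores available (Protocol Table 2), and a responder threshold of 2 units (9.2.1) as a yardstick. Assumed: SD of change 2 to 3, correlation between early and Week 4 change 0.3 to 0.7, dropout 10 to 30%, true mean improvement 2.0.

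**Formula.** Let early and Week 4 improvement be bivariate normal with common SD *s* and correlation *ρ*. Let missingness depend only on early improvement, which is MAR. Then

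bias of the observed-case mean = *ρ* × *s* × *m*,

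where *m* is the mean standardised early improvement of those who remain. If missingness is unrelated to early response, *m* = 0 and there is no bias.

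**Graded dropout.** Let the log-odds of leaving fall by 1 per SD of early improvement. Simulation with 400,000 subjects per scenario gives *m* of about 0.09, 0.17 and 0.25 at 10%, 20% and 30% dropout.

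| SD | Correlation | Dropout | Overstatement (points) |
|---|---|---|---|
| 2 | 0.3 | 10% | 0.3 × 2 × 0.09 = 0.05 |
| 2 | 0.5 | 20% | 0.5 × 2 × 0.17 = 0.17 |
| 2.5 | 0.5 | 20% | 0.5 × 2.5 × 0.174 = 0.22 |
| 3 | 0.5 | 20% | 0.5 × 3 × 0.174 = 0.26 |
| 3 | 0.7 | 30% | 0.7 × 3 × 0.25 = 0.53 |

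A second set of runs used four visits, SD 2.5, correlation 0.5 to 0.7, 10 to 30% dropout after Day 15, and log-odds of 0.3 to 0.6 per point of Day 15 change. It gave 0.09 to 0.57. Together the range is about 0.05 to 0.6.

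**Outer limit.** If exactly the worst early responders leave, *m* = φ(z_d)/(1 − d), where d is the dropout fraction. At 20% dropout this is 0.280/0.8 = 0.35, so with SD 2.5 and correlation 0.5 the overstatement is 0.44. Over the full assumed range it runs from 0.12 to 1.04. This is a bound, not an expectation.

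**Other directions.** With dropout unrelated to response, the simulated bias is 0.00. If better early responders leave more often, *m* changes sign and the mid-range value becomes −0.22.

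**Using the earlier scores.** The regression form of the likelihood estimate is the observed Week 4 mean + slope × (early mean of all − early mean of those observed). Its bias was 0.01 or less in every large-sample scenario. With SD 2.5, correlation 0.5 and about 20% dropout, the bias is +0.01 at n = 20 and 0.00 at n = 40, against +0.23 and +0.22 for the observed-case mean. With two early scores, correlation 0.6 and about a quarter missing, root mean squared error fell from 0.72 to 0.64 at n = 20 and from 0.60 to 0.51 at n = 30.

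**Scale.** With SD 2.5 and an assumed 16 to 32 observed subjects, the standard error is 2.5/√16 = 0.63 to 2.5/√32 = 0.44. The mid-range bias of 0.22 is then about 0.35 to 0.5 of a standard error.

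**The case against.** The strongest reply concerns direction. A reader might infer that subjects without benefit are the ones who stop, so that the mean is overstated. The documents do not say so. The explicit Part C discontinuation rule (Protocol 3.5.2 and 5.2, SAP section 3) is supine hypertension or other adverse events that persist after a dose reduction. Supine hypertension is an excess pressor effect, so those who leave for it may be average or better symptom responders. Lack of efficacy is not among the reasons listed in Protocol 6.4.1, though that list is not exhaustive. Through Day 29 the investigator may also raise the dose, which gives a poor early response another outlet. This stands: the direction is conditional.

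Second, stopping drug need not remove the Week 4 score. The protocol synopsis has early discontinuers return 2 and 4 weeks after the final dose. For a subject who stops near Day 15, the first of these visits falls near Day 29. Whether it counts is unclear, because SAP 6.3 disregards nominal labels for windowing yet limits the tables to data recorded for the scheduled visit. This also stands, and it may reduce the amount missing.

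Third, every magnitude input is assumed, and the likelihood estimator's near-zero bias is partly built in because the simulated data meet its assumptions. That is fair.

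Fourth, the plan exposes some of the problem: tables report N, disposition gives reasons for stopping, and individual plots are planned for all subjects and for completers. These help a reader see missingness but do not correct the mean.

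A reader might also infer from the protocol's abbreviation list, which has MAR, LS and a "heterogeneous banded Toeplitz structure", that a mixed model was planned for Part C and then dropped. The list serves the whole protocol, and Protocol 8.3.2 and 8.4 are blacked out, so it shows nothing about Part C.

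**Conclusion.** The mismatch is real and lies in the text: the SAP states MAR, does not impute, and plans an observed-case mean that MAR alone does not justify. That mean can be biased for the ITT set; the documents do not show that it is. If poor early responders leave more often, and early and Week 4 changes are positively correlated, improvement is overstated by about 0.05 to 0.6 points over the assumed range and by about 0.2 at mid-range values, against a 2-unit responder threshold. Dropout driven by adverse events could produce no bias or understate improvement. Because Part C is descriptive and the mid-range bias is at most about half a standard error at the assumed sample sizes, this is an inexpensive improvement and does not invalidate the plan. The point concerns the continuous mean only, not the responder proportions.

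**What to change.** Keep the descriptive table in SAP 9.2.1 and label it observed-case. Add one supplementary repeated-measures likelihood model of change in OHSA question 1 at Days 8, 15, 22 and 29, with all subjects in one group, visit and baseline score as terms, and a prespecified simple covariance structure suited to a small sample. Report the Day 29 LS mean with a CI, and name it as the estimate that rests on the MAR assumption in 6.4.

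Add two sentences. One should say that, for subjects who stopped drug and have no Day 29 score, the model estimates the value expected had they continued. The other should give the rule for any score collected in the Day 26 to 32 window after stopping, since SAP 6.3 leaves this open.

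The cost is SAP wording and one more table from data already scheduled for collection. The downside is a model fitted in a small sample, with an ordinal 0 to 10 score treated as continuous, as the SAP already does; a poorly chosen covariance structure could bring back some bias.
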